Anaemia, resulting from an inadequate intake of iron and/or low iron bioavailability from the diet as well as from other causes like diseases such as malaria and other micronutrient deficiencies, has been shown to be of public health significance worldwide, particularly in preschool children and women of reproductive age. The Global Burden of Disease study in 2015 estimated that anaemia was the impairment that affected the greatest number of people in 2015 with 2.36 billion individuals affected [4]. Looking at years lost due to disabilities worldwide, iron deficiency anaemia ranks fourth. The 2013 Global Burden of Disease study estimates that 27% of the world's population was anaemic with low-income countries accounting for more than 89% of the burden [5]. Iron deficiency is estimated to be the dominant cause of anaemia worldwide with > 60%. The Kenya National Micronutrient Survey of 2011 [6] and the most recent Demographic and Health Survey in 2014 [3] show that 26% of pre-school children, 26% of women of reproductive age and 42% of pregnant women were anaemic. The prevalence of iron deficiency in children was 21.8% (serum ferritin <12µg/L after being adjusted for inflammation), and that of iron deficiency anaemia was 13.3%. In non-pregnant women of reproductive age, 21.3% were iron deficient (serum ferritin <15µg/L after inflammation adjustment) and 14.0% suffered from iron deficiency anaemia. These values were higher in pregnant women with 36.1% and 26.0%, respectively. The prevalence of vitamin A deficiency based on retinol-binding protein was highest in pre-school age children with 9.2%.

Anaemia can result in several health consequences, starting in very early life such as impaired development of the brain in the foetus and early infancy, impaired immune system and increased infant mortality as well as reduced physical capacity and work performance in adults [7]. Anaemia is in general much more amenable to prevention and treatment than many other conditions such as diabetes or cardiovascular disease but supplementation strategies have failed in many countries. Using an integrated approach delivering micronutrients to pregnant women and young children through a platform that already exists together with other interventions such as WASH that contribute to the prevention of childhood malnutrition might be a promising way forward.

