In round 2, interview questions related to diet and nutrition KAP during pregnancy, dietary diversity, antenatal care, and WASH will be asked. Additionally, MUAC (mid-upper arm circumference) will be measured and a capillary blood sample for measurement of haemoglobin concentration, malaria parasitaemia and micronutrient status will be provided.

Round 3 (Within 24-48 hours after delivery):

The mother-child pair will be visited within 24-48 hours after delivery. The following information will be recorded: delivery date and time, delivery method, recent antenatal care, and early initiation of breastfeeding. The mother will be assessed for MUAC but no blood sampling will be conducted. For the newborn, head circumference, birth weight and birth length, and haemoglobin concentration (from a heelprick) will be measured.

Round 4 (At 6.5 mo ± 1 mo of age of offspring):

This assessment will be conducted when the child turns 6.5 months old. Breastfeeding and other infant and young child feeding indicators, child morbidity, maternal dietary diversity, postnatal care, and WASH information will be gathered. In mothers, MUAC and weight will be measured and haemoglobin concentration and malaria parasitaemia from a capillary sample will be assessed. In

children, length, weight and head circumference will be measured and a capillary blood sample for haemoglobin concentration, malaria parasitaemia and micronutrient status will be provided.

Round 5 (At 24 ± 1mo of age of offspring):

This assessment will be conducted when the child turns 24 months old. Questionnaire-based information on child feeding, child dietary diversity, child morbidity and WASH will be collected. As in round 4, child length, weight and head circumference will be measured and a fingerprick blood sample will be provided for the measurement of haemoglobin concentration, malaria parasitaemia, and micronutrient status. No maternal biomarkers will be collected at this point.

As part of the monthly visits to the participants' households, the CHV will also collect data on intervention adherence and recent morbidity.

[figure not shown]

Figure 2: Timing of assessment rounds for study 1.

[figure not shown]

Figure 3: Detailed procedures for each assessment round in study 1

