7.2 Sample size and randomization

Study 1 and 2:

Some indicators included in study 1, such as maternal haemoglobin, child haemoglobin, and child length-for-age z score (LAZ), are measured more than once in the same study subject over time. This is also the case for haemoglobin and height-for-age z score (HAZ) in the children in study 2. For these indicators, the average change in outcomes in study subjects in the intervention group will be compared to the average change in study subjects in the control group. Other indicators in study 1, such as birth weight and length, are measured only once in each study subject. For these indicators, the average value in the intervention group will be compared to the average value in the control group.

The sample size depends on the size of the desired minimum difference between the intervention group and the control group, which can be detectable with statistical significance. This minimum

difference is expressed as the effect size, which is the difference in the value of the indicator between the two groups to be compared divided by the standard deviation of the indicator. For those outcomes measured more than once, the indicator is the change over time in study subjects. This effect size can be written as follows:

$$\frac{[\text{Mean}(LAZ_{C_x} - LAZ_{C_y})_{\text{Group1}} - \text{Mean}(LAZ_{C_x} - LAZ_{C_y})_{\text{Group2}}]}{\text{Standard deviation}(LAZ_{C_x} - LAZ_{C_y})_{\text{Group1}}}$$

Where C_x and C_y stand for the two measurements of those indicators which are measured twice.

The sample size calculations make the following assumptions: 1) a two-tailed comparison (that is, there is no *a priori* conclusion about which group is higher and which is lower), 2) statistical significance is defined as a p value less than 0.05, 3) the power of the study is at least 0.8, and 4) that the standard deviation of the indicator in both study groups is the same.

Although it is difficult to find highly comparable interventions and their effect sizes for key outcomes put forth, Table 5 below provides an overview of observed effect sizes for somewhat similar interventions and outcomes.

Table 5: Effect sizes in children for similar outcomes and interventions reported in the literature

Description of intervention	Reported outcome	Effect size (95%CI)	Reference
Maternal education on complementary feeding and provision of complementary foods	Weight gain	0.34 (0.11, 0.56)	[35]
	Linear growth	0.26 (0.08, 0.43)	

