7.3.3 Criteria for withdrawal/discontinuation of participants

Study 1:

Pregnant women are free to withdraw themselves or their children from participation in the study at any time. If the pregnant woman is being diagnosed with severe anaemia (haemoglobin (Hb)<70g/L) or severe acute malnutrition (MUAC < 23 cm) at round 1, she will be excluded from participation and will be referred for treatment according to national guidelines to the nearest health centre. If the pregnant woman is being diagnosed with malaria parasitaemia and has an axillary temperature of >37.5°C in round 1, she will be referred for treatment but will continue participating in the study after temporary suspension from interventions if required as assessed by the study physician. If the pregnant woman has an Hb between 70 and 109 g/L in rounds 1 or 2, she will be advised by the study team to go to the hospital for further management. This will be facilitated by CHVs. If the mother, infant or child is being diagnosed with malaria parasitaemia and an axillary temperature of >37.5°C, or severe anaemia (Hb<70g/L), or they suffer from severe acute malnutrition (WHZ<-3 and/or bilateral oedema for child, MUAC < 23 cm for mother) in rounds 2 to 5, affected participants will be referred for treatment according to national guidelines but will continue in the study after temporary suspension from interventions if required as assessed by the study physician. If a child is born with low birth weight (<2500 g) and/or has a Hb < 135 g/L, he/she will be referred for a medical check. Further, study participants will be discontinued from participation in the study in case of any clinical significant adverse event (AE), or any other medical condition or situation that prevents continued participation in the study. If a participant is discontinued no specific follow-up assessments will be conducted other than the follow up until resolution in case of exclusion due to a serious adverse event (SAE). Participants will not be replaced, as a non-consent and dropout rate of 46% prior to reaching 24 months of age is included in the sample size calculation.

Study 2:

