Blood-based secondary outcomes measured in children in study 1 include: Haemoglobin concentration measured at birth and 6 and 24 months of age will be used to assess the change in haemoglobin concentration and proportion with anaemia ($Hb < 11g/dL$). SF (serum ferritin), CRP (C-reactive protein) and AGP (alpha 1- acid glycoprotein) measured at 6 and 24 months of age will be used to assess the proportion with inflammation-adjusted iron deficiency ($SF < 12 \mu g/L$) and the change in proportion with inflammation-adjusted iron deficiency. RBP (retinol binding protein), CRP and AGP measured at 6 and 24 months of age will be used to assess the proportion with inflammation-adjusted vitamin A deficiency ($RBP < 0.7 \mu mol/L$) and the change of proportion with inflammation-adjusted vitamin A deficiency.

Blood-based secondary outcomes measured in pregnant women include: Haemoglobin concentration measured at 34 weeks gestation and 6 months postpartum will be used to assess the change in haemoglobin concentration, the proportion with anaemia ($Hb < 11 g/dL$), and the change in the proportion with anaemia. SF, CRP and AGP measured at 34 weeks gestation will be used to assess the proportion with inflammation-adjusted iron deficiency ($SF < 15 \mu g/L$). RBP, CRP and AGP measured at 34 weeks gestation will be used to assess the proportion with inflammation-adjusted vitamin A deficiency ($RBP < 0.7 \mu mol/L$).

The measurement of haemoglobin will be undertaken on-site using the HemoCue™ device and commercially available control blood. The control blood will be used every morning before measuring any participant's blood sample. SF, RBP, CRP and AGP will be measured using the enzyme linked immunosorbent assay (ELISA) technique at the VitMin laboratory in Germany which is using control samples to assure high quality results. At the different time points, capillary blood will be collected from mothers and eligible children by experienced technicians trained for the techniques used in this evaluation. For children below 12 months of age, capillary blood will be collected by sticking the heel

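### One anaemia cut-off (Hb < 11 g/dL) is fixed for mothers at 34 weeks gestation and at 6 months postpartum, and a change in prevalence is derived across the two states without a postpartum definition

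*Protocol*

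**What the plan says.** Protocol section 8.2 introduces the maternal list with "Blood-based secondary outcomes measured in pregnant women include". The samples are fixed next: "Haemoglobin concentration measured at 34 weeks gestation and 6 months postpartum will be used to assess the change in haemoglobin concentration". The same sentence goes on to "the proportion with anaemia ($Hb < 11 g/dL$), and the change in the proportion with anaemia". One threshold therefore serves both visits and the change between them.

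The postpartum sample is the round 4 visit, when the child is 6.5 months old (section 7.1): "In mothers, MUAC and weight will be measured and haemoglobin concentration and malaria parasitaemia from a capillary sample will be assessed".

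Three other places bear on the point:
- Section 7.3.3 uses the boundary just below 110 g/L in women only during pregnancy: "If the pregnant woman has an Hb between 70 and 109 g/L in rounds 1 or 2". This is a rule for advising women to seek care, not an outcome definition.
- Section 1 reports anaemia separately by state, without giving the cut-offs behind the figures: "26% of women of reproductive age and 42% of pregnant women were anaemic".
- Section 7.2 says how repeated measures are compared: "the average change in outcomes in study subjects in the intervention group will be compared to the average change" in the control group.

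The protocol gives no haemoglobin cut-off for non-pregnant women and does not say why 11 g/dL should apply postpartum.

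**The concern.** Haemoglobin falls in pregnancy as plasma volume expands, which is the usual reason for setting a lower anaemia threshold in pregnancy than outside it. A threshold suited to 34 weeks may therefore be too low at 6 months postpartum. Mothers between it and a higher non-pregnant threshold would then be classed as not anaemic.

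Three results could suffer. The round 4 prevalence would not be comparable with survey figures that use another cut-off. The fall from pregnancy to postpartum would look larger than a state-specific classification would show, in both arms. The between-arm contrast at round 4 would be made on a small tail of the distribution, where a given shift in haemoglobin moves fewer women across the line.

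This is not a detail left to the analysis plan: the protocol itself fixes the visits, the threshold and the derived outcome.

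**Working it through.** The protocol gives no sample size, power or expected rate for maternal anaemia, so there is no figure of its own to reproduce. What follows is an illustration.

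**Inputs from the protocol**
- Cut-off 110 g/L at both visits (section 8.2).
- Anaemia in 26% of women of reproductive age and 42% of pregnant women (section 1).
- 600 women per arm, 95% consent, 80% followed to delivery, 95% of children continued, design effect 1.3, two-sided alpha 0.05 (section 7.2).

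**Assumptions**
- The non-pregnant cut-off C is 115 or 120 g/L.
- 26% of mothers lie below C at round 4, and 42% lie below 110 g/L at 34 weeks.
- Haemoglobin is normal, with SD 10 to 17.5 g/L.

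**Step 1: share counted as anaemic at round 4.** The mean is C − SD × z(0.26), with z(0.26) = −0.643. The counted share is Φ((110 − mean)/SD).

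| C (g/L) | SD (g/L) | Mean (g/L) | Below 110 g/L | Not counted, of 26% |
|---|---|---|---|---|
| 120 | 10 | 126.4 | 5.0% | 21.0 points |
| 120 | 17.5 | 131.3 | 11.2% | 14.8 points |
| 115 | 10 | 121.4 | 12.6% | 13.4 points |
| 115 | 17.5 | 126.3 | 17.6% | 8.4 points |
| 110 | any | – | 26% | 0 |

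**Step 2: apparent fall within an arm.**
- With state-specific cut-offs: 26 − 42 = −16 points.
- With 110 g/L at both visits and C = 120: 11.2 − 42 = −31 to 5.0 − 42 = −37 points. The part due to the cut-off is (31 − 16)/31 = 48% to (37 − 16)/37 = 57%.
- With C = 115: 17.6 − 42 = −24 to 12.6 − 42 = −29 points.

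**Step 3: between-arm comparison.** Effective mothers per arm: 600 × 0.95 × 0.80 × 0.95 / 1.3 = 433.2 / 1.3 = 333. This allows no loss between delivery and round 4. If the intervention does not change haemoglobin, the expected arm difference is zero under any common cut-off. Otherwise, power for two proportions is Φ((|p1 − p2| − 1.96 × SE0)/SE1), with SE0 pooled and SE1 unpooled.

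| C (g/L) | Assumed gain | SD (g/L) | Shares and power at 110 g/L | Shares and power at C |
|---|---|---|---|---|
| 120 | 4 g/L | 13 | 7.9% v 4.3%: 0.50 | 26% v 17.1%: 0.80 |
| 120 | 4 g/L | 15 | 9.5% v 5.7%: 0.45 | 26% v 18.1%: 0.69 |
| 120 | 2 g/L | 13 | 7.9% v 5.9%: 0.18 | 26% v 21.3%: 0.30 |
| 120 | 2 g/L | 15 | 9.5% v 7.4%: 0.16 | 26% v 21.9%: 0.24 |
| 115 | 4 g/L | 13 | 15.2% v 9.1%: 0.68 | 26% v 17.1%: 0.80 |
| 115 | 4 g/L | 15 | 16.4% v 10.7%: 0.58 | 26% v 18.1%: 0.69 |

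**Step 4: the outcome that needs no cut-off.** For mean haemoglobin at round 4, power is Φ(gain / (SD × √(2/333)) − 1.96). A gain of 4 g/L gives 0.98 (SD 13) and 0.93 (SD 15).

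**The case against.** The strongest objection is that the under-count rests on a number the protocol does not contain. It never says that 11 g/dL is specific to pregnancy, and the section 7.3.3 band is a care-seeking rule. The background prevalences come without cut-offs, and the 26% is for women of reproductive age, not for mothers 6 months after delivery in the study area. All of this stands. A reader might infer that the protocol demonstrably under-counts postpartum anaemia. The documents do not support that as a fact, only as a result conditional on a higher non-pregnant cut-off.

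A reader might also infer that the trial's comparison is an artefact. It is not. Section 7.2 compares change between arms, so a fall produced by the classification alone is expected in both arms and cancels when haemoglobin is unaffected. One fixed cut-off also has a logic of its own: the change is then a real shift in the share below 11 g/dL, whereas two cut-offs would put a change of definition inside the measure. That is a reason to report each visit separately, not to leave the postpartum definition unexplained.

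Lastly, the power loss depends on the assumed gain and cut-off. At 2 g/L power is low either way, and at 11.5 g/dL the gap is modest. Change in mean haemoglobin remains an outcome and does not depend on the threshold. These points limit the size of the finding. They do not remove it, because the single rule is on the page without a justification.

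**Conclusion.** The point holds in a limited form. Section 8.2 classifies mothers at 34 weeks and at 6 months postpartum by one cut-off, under a heading that describes only the first group, and derives a change in prevalence across two physiological states.

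On the assumptions above, 8 to 13 percentage points (non-pregnant cut-off 11.5 g/dL) or 15 to 21 points (12 g/dL) of a 26% prevalence would go uncounted at round 4. If 11 g/dL is also the right postpartum threshold, the figure is zero. At 12 g/dL, about half or more of the apparent within-arm fall would come from the classification.

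The distortion is confined to the absolute postpartum prevalence and the within-arm change. For the between-arm comparison the cost is sensitivity, not bias under no effect. The point concerns one dichotomised secondary outcome. The primary outcome, its sample size and the mean haemoglobin comparison are untouched. It is still worth correcting, because section 4.2 names anaemia in mothers in the Study 1 objective and section 10.1 has reports after each round feed programme decisions.

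**What to change.** In section 8.2, for outcome classification only and leaving the rules in section 7.3.3 as they are:
- Keep Hb < 11 g/dL for the 34-week sample.
- Classify the round 4 sample by a stated and justified cut-off for non-pregnant women (conventionally 12 g/dL, to be referenced because the protocol gives none), with the 11 g/dL result as a sensitivity analysis.
- Compare the arms at each visit.
- Drop the pregnancy-to-postpartum change in prevalence, or label it descriptive.
- Reword the heading of the list so that it covers postpartum women.

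The cost is a few lines of text. Haemoglobin values already planned are reclassified, and no new measurement is needed. The downside is that maternal anaemia is no longer summarised as a single change across visits. Change in mean haemoglobin remains as the longitudinal summary.

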8.2.1 Data collection instruments

In all assessment rounds in study 1 and 2, questionnaires will be administered to the participant or the participants' mother/caregiver by previously trained study staff. The type of modules and in which study they are used are summarized in Table 10.

Table 10: Summary of modules used to collect information through questionnaires.

Module	Study 1	Study 2
Household demographics	X	X
Household characteristics	X	X
Maternal education/occupation	X	X
Maternal information on pregnancies and child birth	X	X
Knowledge, attitude and practices (KAP) of dietary and nutrition practices during pregnancy and lactation	X	
Woman dietary diversity	X	
Antenatal care	X	
Postnatal care	X	
Knowledge and consumption of study specific intervention products	X	X
Knowledge and practices on Water, sanitation and hygiene (WASH)	X	X
Initiation of breastfeeding	X	X
Infant and young child feeding indicators (IYCF)	X	X
Child illness	X	X
Adherence	X	X

8.3 Qualitative data collection

Not applicable

8.4 Ethical issues

The decision of the Ethics Committee of the Canton of Zurich (KEK Zurich) regarding a 'no objection statement' as well as the decision of the AMREF's (African Medical & Research Foundation) Ethics & Scientific Review Committee (ESRC) in Kenya concerning the conduct of the study will be made in writing to the Sponsor-Investigator before commencement of this study. The clinical study will only begin once approval (or no objection statement) from both Ethics Committees has been received. Any additional requirements imposed by the ESRC will be implemented to the best possible. Substantial amendments are only implemented following prior approval of the ESRC.

Previously trained 1AF enumerators will explain to each participant in study 1 or to caregivers of children participating in study 2 the nature of the study, its purpose, the procedures involved, the expected duration, the potential risks and benefits and any discomfort it may entail. The information will be provided in the language best understood by the participant/caregiver (Swahili and Luhya). Each participant or caregiver will be informed that the participation in the study is voluntary and that she may withdraw herself or her child from the study at any time and that withdrawal of consent will not affect her and/or her child's subsequent medical assistance and treatment.

The participant will be informed that her and or/her child's medical records may be examined by authorised individuals other than health care staff if need arises.

All participants for the study or caregivers of participating children will be provided a participant information sheet (in Swahili or Luhya) and a consent form describing the study and providing sufficient information for the participant or the caregiver to make an informed decision about their own or their child's participation in the study. In case of illiterate participants/caregivers, the study will be explained in the presence of an impartial witness or read out by the impartial witness that is chosen by the potential study participant. Enough time will be given to the participants/caregivers to decide whether to participate or not. This is particularly important as in some circumstances the caregiver/pregnant woman may need to await her husband's/the head of household's approval for participation.

The participant information sheet and the consent form will be submitted to the KEK Zurich and to the local ESRC to be reviewed and approved. The formal consent of a participant, using the approved consent form, will be obtained before the participant is submitted to any study procedure.

The participant/caregiver of participating children will read, or have read in case of illiterate participants in the presence of an impartial witness, and consider the statement before signing and dating the informed consent form, and will be given a copy of the signed document. The consent will also be signed and dated by the investigator (or his designee) and it will be retained as part of the study records.

For study 1, consent will be taken from the pregnant woman for herself and her offspring. Participants will not receive any compensation for their participation but will receive baby clothing and blankets as a small incentive (both control and intervention group).

For study 2, consent will be taken from the caregiver of the participating child. Participants will not receive any compensation for their participation but will receive blankets as a small incentive (both control and intervention group).

The investigator affirms and upholds the principle of the participant's right to privacy and that they shall comply with applicable privacy laws. Especially, anonymity of the participants will be guaranteed when presenting the data at scientific meetings or publishing them in scientific journals.

Individual subject medical information obtained as a result of this study is considered confidential and disclosure to third parties is prohibited, except in circumstances where medical follow-up is required pursuant to information obtained. Subject confidentiality will be further ensured by utilising subject identification code numbers to correspond to treatment data in the computer files.

Direct access to source documents will only be permitted to the advisory board (see below) members if requested by them. Access to all study related documents (protocol, questionnaires, dataset, randomization code, etc.) during and after the study will be managed by the sponsor-investigator who will delegate access to the respective documents.

Data from the two studies will be stored on CommCare's secure cloud server. Only selected 1AF Kenya Monitoring & Evaluation staff and GroundWork investigators will have access to the password-protected data on CommCare. They will be able to access the data as it is uploaded from the tablets. De-identified data will be downloaded regularly on password-protected servers for monitoring purposes, which will serve as a back-up.

The serum samples collected for the analysis of micronutrient status will be stored until final lab results are received and validated from the VitMin Lab. Six months after the results are considered as final, the samples will be destroyed. The duplicate sample, which will be held as back-up samples in Kenya in case something happens to the samples during shipment to Germany, will also be destroyed six months after results are considered final.

The investigators suggest having an advisory board that will review the protocol, tools and baseline reports, followed by moderated teleconferences to discuss course correction. They would also review the final reports. The following people have accepted to be on the advisory board:

[name] [name], KEMRI-Wellcome Trust, Kilifi, Kenya
[name], King's College London, London, UK
[name], University of Ghana, Accra, Ghana

